12. Agreement not to donate blood or blood products during the study and for at least 9 months *or as per approved local prescribing information for vismodegib (where available), whichever is longer, after discontinuation of vismodegib*. Because vismodegib has been detected in seminal fluid, in addition for men, agreement not donate sperm during the study or for at least 2 months *or as per approved local prescribing information for vismodegib (where available), whichever is longer, after discontinuation of therapy*

NOTE: The waiting time for blood donations was changed from 7 to 9 months or as per approved local prescribing information, whichever is longer, after all patients were enrolled in the study.

13. Life expectancy > 12 weeks
14. Negative serum pregnancy test within 7 days prior to commencement of dosing in premenopausal women. Women of non-childbearing potential may be included if they are either surgically sterile or have been postmenopausal for ≥ 1 year

Exclusion Criteria:

1. Inability or unwillingness to swallow capsules
2. Pregnancy or lactation
3. Concurrent non-protocol-specified anti-tumor therapy (e.g., chemotherapy, other targeted therapy, radiation therapy, or photodynamic therapy, including participation in an experimental drug study; note that treatment breaks up to 8 weeks for radiation therapy are allowed [see Section 6.1.1])
4. Completion of most recent anti-tumor therapy less than 21 days prior to initiation of treatment
5. Uncontrolled medical illnesses such as infection requiring treatment with intravenous antibiotics
6. History of other disease, metabolic dysfunction, physical examination finding, or clinical laboratory finding giving reasonable suspicion of a disease or condition that contraindicates use of an investigational drug or that might affect interpretation of the results of the study or that renders the patient at high risk from treatment complications
7. Assessed by the Investigator to be unable or unwilling to comply with the requirements of the protocol
8. Patients with one of the following rare hereditary

conditions: galactose intolerance, primary hypolactasia, or glucose-galactose malabsorption

LENGTH OF STUDY

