- Tumor assessment (the majority of the patients in this study have locally advanced BCC and, in this disease setting, measurable tumors are accessible to evaluation by physical examination). Objective responses using RECIST, v1.1 should be confirmed by repeat assessments at least 4 weeks after initial documentation of response:
 - Measurable tumors accessible to evaluation by physical examination should be assessed every 4 to 8 weeks throughout the study from the time of the first dose, regardless of dosing delays

- If assessment requires imaging, baseline CT and/or MRI should be performed within a maximum of 28 days prior to the first dose of study drug and, if such scans demonstrate evidence of disease, follow-up imaging studies (CT and/or MRI) should be performed every 8 to 16 weeks from the time of the first dose, regardless of dosing delays, or per institutional standards. The same imaging technique (CT or MRI) should be used for each patient throughout the study
- In metastatic BCC patients (newly enrolled after approval of the Study Protocol, version 4.0), imaging at baseline (CT and/or MRI scan) should be performed within a maximum of 28 days before the first dose. Follow-up imaging studies (CT and/or MRI scan) should be performed every 8 weeks (± 5 days) from the time of the first dose, regardless of dosing delays. The same imaging technique (CT or MRI) should be used for each patient throughout the study
- Other imaging techniques may be performed as clinically indicated, but should not be used for determining tumor response
- Patients with non-measurable disease at baseline should be assessed for disease progression when clinically indicated and in accordance with standard clinical practice. For metastatic patients, assessment of non-measurable disease should be according to RECIST version 1.1.
- In selected sites, patients will complete the Skindex-16 Quality of Life questionnaire after Cycle 1 and after Cycle 6 (i.e., after 6 months of treatment) for the patients still on study (see Main Protocol Section 5.5. and Appendix 5)
- Patients with metastatic BCC (newly enrolled after approval of the Study Protocol, version 4.0) will complete the M.D. Anderson Symptom Inventory (see Main Protocol Section 5.6 and Appendix 6) at every visit, prior to having any other assessments performed

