4.3 EXCLUSION CRITERIA

A patient will be excluded if the answer to any of the following statements is "yes."

1. Inability or unwillingness to swallow capsules
2. Pregnancy or lactation
3. Concurrent non-protocol-specified anti-tumor therapy (e.g., chemotherapy, other targeted therapy, radiation therapy, or photodynamic therapy, including participation in an experimental drug study; note that treatment breaks up to 8 weeks for radiation therapy are allowed [see Section 6.1.1])
4. Completion of most recent anti-tumor therapy less than 21 days prior to initiation of treatment
5. Uncontrolled medical illnesses such as infection requiring treatment with intravenous antibiotics
6. History of other disease, metabolic dysfunction, physical examination finding, or clinical laboratory finding giving reasonable suspicion of a disease or condition that contraindicates use of an investigational drug or that might affect interpretation of the results of the study or that renders the patient at high risk from treatment complications
7. Assessed by the Investigator to be unable or unwilling to comply with the requirements of the protocol
8. Patients with one of the following rare hereditary conditions: galactose intolerance, primary hypolactasia, or glucose-galactose malabsorption

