4.4.2 Excluded Therapy and Potential Interactions With Concomitant Drugs

Coadministration of St John's wort (*Hypericum perforatum*) and other concomitant anti-tumor therapies are prohibited during this study.

Medicinal products that alter the pH of the upper gastrointestinal tract (e.g., proton pump inhibitors, H₂-receptor antagonists, and antacids) may alter the solubility of vismodegib and reduce its bioavailability. However, no formal clinical trial has been conducted to evaluate the effect of gastric pH altering agents on the systemic exposure of vismodegib. Increasing the dose of vismodegib when co-administered with such agents is not likely to compensate for the loss of exposure. Therefore, when vismodegib is co-administered with a proton pump inhibitor, H₂-receptor antagonist, or antacid, systemic exposure of vismodegib may be decreased, and the effect on efficacy of vismodegib is unknown. Patients with achlorhydria would be subject to the same potential effect.

In vitro studies indicate that vismodegib is a substrate of the efflux transporter P-glycoprotein (P-gp) and the drug metabolizing enzymes CYP2C9 and CYP3A4. When vismodegib is co-administered with medicinal products that inhibit P-gp (e.g., clarithromycin, erythromycin, azithromycin, verapamil, cyclosporine), CYP2C9 (e.g., amiodarone, fluconazole, miconazole), or CYP3A4 (e.g., boceprevir, clarithromycin, coniraptan, indinavir, traconazole, ketoconazole, lopinavir/ritonavir, nelfinavir, posaconazole, ritonavir, saquinavir, telaprevir, telithromycin, voriconazole), systemic exposure of vismodegib and incidence of adverse events of vismodegib may be increased. When vismodegib is administered with CYP inducers (e.g., rifampin, carbamazepine, phenytoin, St. John's wort) exposure to vismodegib may be decreased.

Results of a drug-drug interaction study conducted in cancer patients demonstrated that the systemic exposure of ethinyl estradiol and norethindrone is not altered when co-administered with vismodegib. However, the interaction study was of only 7 days duration, and it cannot be excluded that vismodegib upon longer treatment is a mild inducer of enzymes that metabolize ethinyl estradiol contraceptive steroids. This modest induction might lead to a decrease in systemic exposure of this contraceptive steroid, and thereby reduced contraceptive efficacy.

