6.1.1 Dose Modifications, Interruptions, and Delays

No dose reductions will be allowed in this study.

Treatment with vismodegib may be interrupted for up to:

- Eight weeks if a patient becomes temporarily unable to swallow capsules
- Eight weeks for an intolerable toxicity finding

Any other proposed reasons for interruption of treatment should be discussed in advance with the Medical Monitor. The Medical Monitor must be consulted in all cases where study drug will be interrupted.

Intolerable toxicities are defined as new (not present at baseline) Grade 3 or 4 AEs considered related to vismodegib that are likely to be life-threatening or irreversible and, in the opinion of the Investigator, the risk outweighs the benefit of continued treatment with vismodegib. The following AEs are not considered intolerable:

- Grade 3 or 4 events that in the opinion of the Investigator are more likely related to ongoing or recent procedures or concomitant medications other than vismodegib
- Hematologic or metabolic/chemistry laboratory abnormalities that are found on routine testing and are not considered clinically significant
- Musculoskeletal abnormalities, skin ulceration, fracture, debridement or wound care, and dental or periodontal disease related to underlying medical conditions (e.g., basal cell carcinoma and nevoid basal cell carcinoma [Gorlin] syndrome)
- Nausea, vomiting, or diarrhea that are adequately controlled after optimization of medical management
- Grade 3 infection that is transient and treatable or manageable
- Grade 3 sterility
- Asymptomatic thromboembolism found incidentally on imaging and managed with anti-coagulation therapy

Patients with an asymptomatic or tolerable severe AE may continue to receive study drug provided the AE is manageable and the patient and the Investigator agree that continued study participation is acceptable.

If a patient experiences two treatment interruptions, the Medical Monitor must be consulted before the patient can resume treatment.

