- Best Overall Response would be Stable Disease (SD) if subject's best overall response is not CR or PR, and there is at least one response assessment of CR, PR or SD with minimum of 51 days after First Dose Date without any Progressive Disease (PD) in between.
- Best Overall Response would be Progression Disease (PD) if subject's best overall response is not CR, PR, or SD, and if there is at least one response assessment of PD.
- Best Overall Response would be Not Evaluable (NE) if subject's best overall response is not CR, PR, SD, or PD, and there is at least one response assessment of NE.
- BOR would be PD if PD occurred before satisfying any of the above criteria of Best Overall Response.
- Patients who achieve best overall response of CR or PR are considered a responder.
- Best overall response rate is defined as the number of patients with a CR or PR observed at two consecutive assessments  $\geq 4$  weeks apart ( $\geq 23$  days) divided by the total number of patients with histologically confirmed measurable disease at baseline.
- N in column headings is the number of patients with a measurable or non-measurable disease at baseline and histologically confirmed BCC. Percentages are calculated based on the number of patients with a measurable disease at baseline and histologically confirmed BCC.
- Display only Responder and 95%CI for Best Overall Response Rate.

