### Programming Note:

- Progression-Free Survival is defined as the interval between the date of first treatment and the date of Progressive Disease or Death.
- Patients without disease progression or death will be censored at the date of last tumour assessment.
- N would be the number of patients with a measurable or non-measurable disease at baseline and histologically confirmed BCC.
- Percentages are based on N.
- Patients with a measurable or non-measurable disease at baseline and histologically confirmed BCC are included in the analysis.

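### Response, duration-of-response and PFS rules ignore on-study radiotherapy, which exclusion criterion 3 permits but other sections do not, so ORR can be biased upward by an unknown amount

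*Protocol*

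**What the plan says.** Exclusion criterion 3 appears in the protocol synopsis and in Section 4.3. It names radiation therapy among barred concurrent treatments and then makes an allowance, with a reference to Section 6.1.1: "note that treatment breaks up to 8 weeks for radiation therapy are allowed".

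Section 6.1.1 permits interruptions of up to eight weeks for two reasons. One is "Eight weeks if a patient becomes temporarily unable to swallow capsules"; the other is intolerable toxicity. Radiotherapy is not listed. For the rest it states: "Any other proposed reasons for interruption of treatment should be discussed in advance with the Medical Monitor". Section 4.4.2 says that "other concomitant anti-tumor therapies are prohibited during this study", with no exception for radiotherapy.

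Tumour measurement does not pause with the drug. Under Treatment Phase Assessments in the synopsis, measurable tumours accessible to physical examination "should be assessed every 4 to 8 weeks throughout the study from the time of the first dose, regardless of dosing delays". Imaging follows its own interval, also irrespective of dosing delays.

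The SAP derives best overall response from the sequence of assessments alone: CR or PR must be seen on two assessments at least 23 days apart. Then: "Patients who achieve best overall response of CR or PR are considered a responder". For PFS, "Patients without disease progression or death will be censored at the date of last tumour assessment", and duration of response is censored in the same way. Protocol Section 8.2.1.1 makes ORR the main efficacy variable of interest and also has no radiotherapy rule.

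**The concern.** If a target lesion is irradiated during a permitted break and shrinks by 30% or more, and the shrinkage is confirmed, the patient can enter the numerator of the vismodegib ORR. If an irradiated lesion would otherwise have grown, progression is recorded later or not at all. The trial has one arm, so no comparator separates the effect of local radiotherapy from that of the drug. No hypothesis test is planned either. The point estimate and its interval are the efficacy result, and a reader will take them as the effect of vismodegib.

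**Working it through.** **1. Is the allowance consistent?** Exclusion criterion 3 permits the break and refers to Section 6.1.1. Section 6.1.1 does not contain it and sends unlisted reasons to the Medical Monitor. Section 4.4.2 prohibits other anti-tumor therapy outright. Read together, they leave unclear whether on-study radiotherapy is permitted, needs case-by-case discussion, or is a deviation.

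**2. Does any other rule remove post-radiotherapy data?**
- Protocol Appendix 1, Section 1.1.3, covers lesions treated locally in the past, and only for measurability at baseline.
- The synopsis (Length of Study) ends follow-up when another anti-cancer therapy begins, but only for patients who have discontinued study drug. A patient on a temporary break has not.
- The SAP requires confirmation at least 23 days apart and sets best overall response to PD if PD occurs before another criterion is met. Both limit what counts, but neither mentions radiotherapy. The PD rule is also loosely worded. A patient may meet the SD criterion (at least 51 days from first dose), then progress, continue on drug as Section 6.1 allows after consultation, be irradiated, and reach a confirmed PR. That patient is not clearly excluded.

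**3. Inputs for size.**
- Cohort sizes: 1119 locally advanced and 96 metastatic (SAP, Summary of Deaths). The ORR denominators are patients with measurable, histologically confirmed disease, so these are upper limits.
- Reference ORRs, for illustration only: 27/63 = 42.9% and 10/33 = 30.3% (the pivotal phase II trial described in the protocol background).
- Interval: two-sided 95% Clopper-Pearson, as the SAP specifies. Lower limit = Beta quantile (0.025; x, n − x + 1); upper limit = Beta quantile (0.975; x + 1, n − x).
- Number irradiated on study: not given.

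**4. Check of the method.** The plan gives no precision figure for ORR. Its one precision statement, for adverse events in Section 8.3, is 8.4%–11.8% for 120/1200. The formula gives 8.36%–11.84%, which agrees.

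**5. Effect of one patient.** 1/1119 = 0.09 points; 1/96 = 1.04 points. With smaller true denominators each is larger, so these are minimum values.

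**6. Range under assumptions.** Let f be the share of measurable-disease patients who would not have responded and are irradiated on target lesions, and r the share of those who then reach a confirmed CR or PR. The shift in ORR is f × r. With f from 1% to 10% and r from 25% to 100%, it runs from 0.01 × 0.25 = 0.25 points to 0.10 × 1.00 = 10 points.

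| Cohort | f | r | Shift (points) | ORR | 95% CI |
|---|---|---|---|---|---|
| Locally advanced, N = 1119 | 0 | – | 0 | 42.9% | 40.0–45.9% |
| | 1% | 50% | 0.5 | 43.4% | 40.4–46.3% |
| | 5% | 50% | 2.5 | 45.4% | 42.5–48.4% |
| | 5% | 100% | 5.0 | 47.9% | 44.9–50.9% |
| Metastatic, N = 96 | 0 | – | 0 | 30.3% | 21.3–40.4% |
| | 5% | 100% | 5.0 | 35.3% | 25.9–45.8% |
| | 10% | 100% | 10.0 | 40.3% | 30.7–51.1% |

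Intervals use the nearest whole number of responders. In the locally advanced cohort the half-width is (45.86 − 39.97)/2 = 2.9 points, or about 0.029 × 1119 ≈ 33 patients. With 480 responders there are 1119 − 480 = 639 non-responders, so a shift of one half-width would require about 33/639 = 5% of them to become confirmed responders through radiotherapy. In the metastatic cohort the half-width is (40.43 − 21.25)/2 = 9.6 points, or about 9 of 67 non-responders.

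**The case against.** Several counter-arguments have force.

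- *Irradiation of target lesions may be rare.* Inclusion criterion 6 requires locally advanced patients to have progressed after radiotherapy, or radiotherapy to be contraindicated or inappropriate. That cohort is 1119 of 1215 patients (92%). Nothing says that a target lesion, or even BCC, would be irradiated during a break. This stands and is why no size can be asserted. The criterion does not apply to metastatic patients, where each patient weighs most.
- *Efficacy is secondary.* Safety is the primary objective, and no error rate, sample size or decision rule depends on ORR. This stands and limits the importance of the point.
- *Radiotherapy is partly visible already.* Reasons for treatment breaks, concomitant therapies and major protocol violations are all reported. True, but none of these outputs is linked to response.
- *Other rules may exist.* The SAP cites the DAP M3 and the LoPO, which are not among the documents reviewed and may address this.

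A reader might also infer more than the documents support. It is not the case that every later CR or PR counts: an unconfirmed response does not, and earlier PD can block one. Nor do the documents show that ORR *is* biased. That needs irradiated target lesions in patients who would not otherwise have responded, and their number is unknown. A single direction of bias is likewise not shown for duration of response and PFS. Delayed PD in an irradiated lesion lengthens both. But the patient is off drug during the break, so other lesions may progress, and radiotherapy-assisted responders with short responses could lower the median duration.

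**Conclusion.** The point holds as a gap in the analysis rules together with a contradiction in the protocol. Exclusion criterion 3, Section 6.1.1 and Section 4.4.2 do not agree on radiotherapy during treatment and must be reconciled. As the SAP is written, a confirmed CR or PR after on-study irradiation can be credited to vismodegib. ORR can therefore be biased upward, and duration of response and PFS can be distorted.

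The amount is unknown. Each affected responder adds at least 0.09 points (locally advanced) or 1.04 points (metastatic), taking the safety cohort sizes as upper limits for the denominators. The tabulated shifts rest on assumed values of f and r that have no source in the documents. The effect may be negligible; the plan as it stands gives no way to tell.

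**What to change.** 1. In the protocol, reconcile exclusion criterion 3 (synopsis and Section 4.3) with Sections 6.1.1 and 4.4.2. Which rule should apply is a clinical matter for the sponsor.
2. In the SAP, add a table by cohort giving the number of patients with on-study radiotherapy and the number whose first or confirming CR/PR falls after it. The sources are the *Reason for breaks in treatment* and *Concomitant Medications and Therapies* CRF pages, both of which the SAP already uses.
3. Add a sensitivity analysis of ORR in which both the qualifying and the confirming assessment must precede on-study radiotherapy for BCC. Restrict this to irradiated target lesions if the treated site is recorded; the SAP does not show that it is.
4. Add sensitivity analyses of duration of response and PFS, censored at the last evaluable assessment before that radiotherapy.

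The main analysis can stay as it is. Classing every patient whose first response follows any radiotherapy as a non-responder would penalise patients irradiated elsewhere, and would still miss a response that began before radiotherapy and was confirmed only after it.

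The cost is one derived date and a little extra programming. The sensitivity ORR may be slightly lower than the main one. If few patients are affected, the table shows that the reported ORR is robust on this point.
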